11 BIOSTATISTICAL ANALYSIS

11.1 Sample Size Considerations

The primary endpoint of this phase II study is progression free survival (PFS). The primary analysis will compare the control arm (lenalidomide plus placebo) versus the pooled allogenic myeloma vaccine arms (with and without Prevnar). In a prior study, the median PFS for patients on Len containing therapy was 17.9 months. Patients will be accrued over the course of 2 years with a minimum follow-up of 3 years (i.e. all patients will have 3-5 years of follow-up). A sample size of 54 patients (18 placebo vs 36 allogenic myeloma) would provide 80% power to detect an increase in the median PFS from 18 months in the control arm to 42.8 months in the pooled vaccine arm ($HR = 0.4199$) based upon a log-rank test assuming a two-sided type I error rate of 10% and a loss to follow-up rate of 1% per year (5% overall). The accrual rate is expected to be 2.3 per month. Due to the small sample size, no interim efficacy analysis is planned at this time.

Our principal secondary endpoints will be conversion from “near CR” (M-spike at or below 0 but IFE positive), to “true CR” (IFE negative), and conversion from MRD positive status to MRD negative status. The trial will accrue patients for a total $n=18$ per arm at single center for a period two years, while trial duration for every patient enrolled will be 3 years. The analysis will be performed on the intention to treat population.

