Tumor immunology assessments will be made at baseline and on day 14 of cycles 3, 6, and 12 (the 1-year assessment). At each time point, graphical (e.g. boxplots over time, spaghetti plots) and numeric (e.g. median, range, proportion) summaries will be used to explore the continuous (e.g. T cell populations) and binary (e.g. tumor specific immunity) outcomes. If appropriate, transformations (e.g. log) will be used to address skewness in the data. Cross-sectional comparisons will be made using t-tests, Kruskal-Wallis tests, or linear regression and Chi-squared tests, Fisher’s exact test, or logistic regression for continuous and categorical outcomes, respectively. Generalized estimating equations and mixed effects models will be used to formally model the behavior over time and compare treatment groups and/or risk factors while adjusting for repeated measurements within each individual. The association between baseline tumor measurement as well as changes in tumor measurements over time and clinical outcomes will be assessed using Cox proportional hazards models.

Toxicity will be scored using NCI CTC Version 4.0 for toxicity and adverse events. All toxicities will be summarized overall, by treatment group, and within subgroups of interest (e.g. true CR status, MM type). The number of toxicities and number of affected patients will be tabulated by type, grade, and relatedness to study treatment (overall and for each treatment). In addition to counts and proportions, the toxicity rates will be modeled and compared between treatment groups and subgroups of interest using Poisson regression or Negative Binomial regression, as appropriate.

11.3 Toxicity Stopping Guidelines:

The proportion of unacceptable toxicities will be continuously monitored in each arm separately. Unacceptable toxicities include hematologic toxicities of lenalidomide: low neutrophils (ANC <1000) and low platelets (<50K), for which we would hold the vaccine administration, as well as vaccine related toxicities which include: grade 3/4 local reactions (erythema, swelling, pain) and systemic symptoms (fevers, rash) (Refer to **7.6.1** and **7.6.2** for guidelines on attribution of toxicities).

Unacceptable toxicities as scored using **NCI CTCAE V5.0** include:

- Any laboratory or clinical organ dysfunction \geq Grade 3
- Abnormalities of coagulation (prolonged prothrombin, partial thromboplastin and clotting times \geq Grade 3)
- Autoimmune disease reactivation or development \geq Grade 2

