- Immune system disorders including myalgias or headaches \geq Grade 3
- Immune system disorders including allergic or hypersensitivity reactions such as rash, or fever \geq Grade 3
- Immune system disorders including anaphylaxis or anaphylactoid reactions (eg. Wheezing, urticarial, hypotension) \geq Grade 3
- General disorders and administration site conditions including injection site reactions such as tenderness with or without associated symptoms (e.g., warmth, erythema, itching, and malaise) \geq Grade 3
- Any other undefined or unanticipated adverse event \geq Grade 3
- Any death on study

If the levels of unacceptable toxicities is too high (i.e. a high probability that they exceed the maximum threshold of 30%), then enrollment will be suspended pending review by the PI, DSMB, and Celgene. Any death on study within 30 days of GVAX administration will lead to suspension of enrollment pending review by the PI, DSMB, and Celgene.

A Bayesian stopping guideline will be used to assess the level of unacceptable toxicity. We expect the rate of unacceptable toxicities to be 25%. Hence a Beta(1, 3) prior was used. After the first three patients are recruited, toxicity will be monitored continuously. Accrual will be suspended if the probability that the unacceptable toxicity rate exceeds 30% is 0.70 or higher. Table 11.1 shows the number of toxicities needed to halt accrual.

Table 11.1. The number of toxicities needed to trigger stopping guidelines throughout the course of the study.

Number of Subjects Per Treatment Arm	Number of toxicities needed to trigger re-evaluation
3-4	3
5-7	4
8-10	5
11-13	6
14-16	7
17-18	8

The operating characteristics of these stopping guidelines were generated based upon 5000 simulations (Table 11.1).

Table 11.2. Probability of triggering stopping guidelines based upon range of underlying toxicity rates.

True Toxicity (DLT) Risk	Prob. Declare Treatment Too Toxic	Avg. Sample Size
0.05	<0.1%	18.0
0.10	0.4%	18.0
0.15	2.7%	17.7
0.20	7.6%	17.2
0.25	15.2%	16.5
0.30	27.7%	15.4
0.35	44.0%	13.8
0.40	59.5%	12.3
0.45	74.2%	10.7

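### The written toxicity stopping rule (Beta(1,3) prior, 0.70 cut-off) does not produce Table 11.1: it pauses accrual one toxicity earlier at 11 of 16 arm sizes, and at a 25% rate pauses an arm 33% of the time, not 15.2%

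*Combined protocol and SAP*

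**What the plan says.** Section 11.3 (Toxicity Stopping Guidelines) defines the monitoring rule completely:

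- Unit: "The proportion of unacceptable toxicities will be continuously monitored in each arm separately". Section 11.1 sets the arm size at 18.
- Prior: the expected rate of unacceptable toxicity is 25%, and "Hence a Beta(1, 3) prior was used".
- Looks: "After the first three patients are recruited, toxicity will be monitored continuously".
- Action: "Accrual will be suspended if the probability that the unacceptable toxicity rate exceeds 30% is 0.70 or higher".

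It then says "Table 11.1 shows the number of toxicities needed to halt accrual". The tabulated counts are 3 toxicities at 3–4 patients, 4 at 5–7, 5 at 8–10, 6 at 11–13, 7 at 14–16 and 8 at 17–18.

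Table 11.2 reports the operating characteristics from 5000 simulations. At a true rate of 25% it gives a 15.2% chance of triggering and an average arm size of 16.5; at 40% it gives 59.5% and 12.3.

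**The concern.** The prior, the 30% threshold, the 0.70 cut-off and the looks together fix the stopping counts, so Table 11.1 should follow from the text by direct calculation. It does not, and the two can require opposite actions on the same data. If 2 of the first 3 patients in a vaccine arm have an unacceptable toxicity, a reader who computes the posterior suspends enrollment and a reader who looks up the table does not.

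This is the plan's quantitative safety rule for a cellular vaccine in arms of 18, and Table 11.2 is the evidence given for how that rule performs. If the text is followed, pauses at the expected rate are about twice as frequent as Table 11.2 says. If the table is followed, an arm with excessive toxicity is caught less often, and later, than the written 0.70 criterion implies.

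**Working it through.** **Inputs (Section 11.3; arm size from 11.1).** Prior Beta(1,3); threshold 0.30; cut-off 0.70; looks after each patient from n = 3 to n = 18, which is 16 arm sizes; each arm monitored separately.

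**Posterior.** With x toxicities in n patients the posterior is Beta(1+x, 3+n−x). For integer parameters, P(rate > 0.30) = P(Bin(n+3, 0.30) ≤ x).

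Worked example, 2 of 3: P(Bin(6, 0.30) ≤ 2) = 0.7⁶ + 6(0.3)(0.7⁵) + 15(0.3²)(0.7⁴) = 0.1176 + 0.3025 + 0.3241 = 0.744. This exceeds 0.70, so the text suspends. Table 11.1 requires 3.

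**Stopping counts.** The smallest x with posterior probability at least 0.70, against Table 11.1. The last column is the posterior probability at one toxicity below the tabulated count.

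| n | Written rule | Table 11.1 | P(rate > 0.30) at table count − 1 |
|---|---|---|---|
| 3 | 2 | 3 | 0.744 |
| 4 | 3 | 3 | 0.647 |
| 5 | 3 | 4 | 0.806 |
| 6 | 3 | 4 | 0.730 |
| 7 | 4 | 4 | 0.650 |
| 8 | 4 | 5 | 0.790 |
| 9 | 4 | 5 | 0.724 |
| 10 | 5 | 5 | 0.654 |
| 11 | 5 | 6 | 0.780 |
| 12 | 5 | 6 | 0.722 |
| 13 | 6 | 6 | 0.660 |
| 14 | 6 | 7 | 0.775 |
| 15 | 6 | 7 | 0.722 |
| 16 | 7 | 7 | 0.666 |
| 17 | 7 | 8 | 0.772 |
| 18 | 7 | 8 | 0.723 |

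The two differ at n = 3, 5, 6, 8, 9, 11, 12, 14, 15, 17 and 18: 11 of 16 sizes, always by one, with the table always the more permissive.

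**Not rounding.** The written rule's counts stay the same for any cut-off from 0.666 to 0.721, so neither rounding nor reading the criterion as strictly greater than 0.70 explains the gap. With Beta(1,3), Table 11.1 needs a cut-off above 0.806 and no higher than 0.818.

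**Operating characteristics.** An exact forward recursion over n = 3 to 18 carries the probability of each toxicity count forward and removes the paths that reach the limit. It gives the per-arm chance of a pause:

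| True rate | Table 11.2 as printed | Exact, Table 11.1 counts | Exact, written rule |
|---|---|---|---|
| 20% | 7.6% | 7.5% | 20.1% |
| 25% | 15.2% | 16.1% | 33.5% |
| 30% | 27.7% | 28.6% | 48.8% |
| 35% | 44.0% | 43.8% | 63.9% |
| 40% | 59.5% | 59.6% | 77.1% |
| 45% | 74.2% | 73.8% | 87.0% |

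The Table 11.1 counts reproduce Table 11.2; the written rule does not. Average arm size at 25% is 16.4 for the table's counts (printed 16.5) and 14.1 for the written rule. At 40% it is 12.3 (printed 12.3) and 9.1.

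Monte Carlo error in 5000 runs does not bridge the gap. At 25%, the standard error under the table's counts is √(0.161 × 0.839 / 5000) = 0.0052, so 15.2% is (0.161 − 0.152)/0.0052 ≈ 1.8 standard errors away. Under the written rule it is √(0.335 × 0.665 / 5000) = 0.0067, and 15.2% is about 27 standard errors away. A separate 200,000-run simulation of the written rule gave 33.4%.

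**First look at n = 4.** If monitoring starts with the fourth patient, the written rule still pauses an arm 29.3% of the time at a 25% rate and 75.1% at 40%.

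**Across three independent arms, all at 25%.** The chance that at least one pauses is 1 − (1 − 0.3345)³ = 70.5% under the written rule and 1 − (1 − 0.1613)³ = 41.0% under the table. The documents give no placebo rate. If it is assumed to be 10% to 20%, with both vaccine arms at 25%, the ranges are 57–65% and 30–35%.

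**The case against.** The strongest reply is that study staff will use the count table, since the text points to it. Table 11.2 is then essentially right (16.1% exact against 15.2% printed at a 25% rate), and the 33% applies only if someone computes the posterior from the text. That condition is fair. But the sentence is worded as binding and the table is offered as its consequence, so nothing tells staff or the DSMB which governs when 2 of 3 patients have a toxicity.

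A second reply is that the consequence is limited. A trigger leads to review by the PI, DSMB and Celgene, not to termination. Any death within 30 days of vaccination suspends enrollment separately, and the DSMB reviews the trial at least annually. This is correct and caps the severity, but it does not resolve the contradiction.

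Third, the calculation treats each patient's toxicity status as known when that patient is counted. Vaccination continues to 36 months, so actual pause rates will differ. This applies to both versions and does not account for the gap between them.

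Finally, several prior and cut-off pairs reproduce Table 11.1; Beta(2,6) with 0.75 is another. The documents therefore cannot show which input was misstated, and the sponsor has to say.

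**Conclusion.** The concern holds. The written rule and Table 11.1 are different rules, one toxicity apart at 11 of 16 arm sizes, and Table 11.2 belongs to the table. Under the written rule an arm at the expected 25% rate pauses 33.5% of the time rather than the stated 15.2%. Under the table, an arm at 40% is paused 59.6% of the time after an average of 12.3 patients, rather than 77.1% after 9.1.

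The stopping counts follow from Section 11.3 without further assumption. The pause probabilities assume looks after each patient from n = 3 and toxicity status known at each look; the three-arm figures also assume independent arms. This should be corrected. It affects safety monitoring and its reported performance, not the efficacy analysis.

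**What to change.** The sponsor should confirm which rule generated the tables and which it wants, then state one rule.

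- **Keep the tables.** Tables 11.1 and 11.2 agree with each other, so the smallest change is to the text: a 0.81 cut-off with Beta(1,3), or a Beta(3,9) prior (also mean 25%) with the 0.70 cut-off. Each reproduces Table 11.1 at all 16 sizes. This changes one sentence and keeps the 59.5% detection at a 40% rate.
- **Keep the text.** Replace Table 11.1 with 2 toxicities at 3 patients, 3 at 4–6, 4 at 7–9, 5 at 10–12, 6 at 13–15 and 7 at 16–18, and rerun Table 11.2. Detection at a 40% rate rises to about 77%, and about one arm in three pauses at the expected 25% rate.

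The choice is between fewer pauses and earlier detection. In the same edit, say whether a trigger in one arm pauses accrual to all three. Neither option changes the sample size or the analysis.

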12 REGULATORY CONSIDERATIONS

121 Institutional Review Board/Ethics Committee approval

The protocol for this study has been designed in accordance with the general ethical principles outlined in the Declaration of Helsinki. The review of this protocol by the IRB/EC and the performance of all aspects of the study, including the methods used for obtaining informed consent, must also be in accordance with principles enunciated in the declaration, as well as ICH Guidelines, Title 21 of the Code of Federal Regulations (CFR), Part 50 Protection of Human Subjects and Part 56 Institutional ReviewBoards.

The Primary Investigator will be responsible for preparing documents for submission to the relevant IRB/EC and obtaining written approval for this study. The approval will be obtained prior to the initiation of the study.

The approval for both the protocol and informed consent must specify the date of approval, protocol number and version, or amendment number.

Any amendments to the protocol after receipt of IRB/EC approval must be submitted by the Investigator to the IRB/EC for approval. The Investigator is also responsible for notifying the IRB/EC of any serious deviations from the protocol, or anything else that may involve added risk to subjects.

Any advertisements used to recruit subjects for the study must be reviewed and approved by the IRB/EC prior to use.

122 Informed consent

The Primary Investigator must obtain informed consent of a subject or his/her designee prior to any study related procedures as per GCPs as set forth in the CFR and ICH guidelines.

Documentation that informed consent occurred prior to the subject's entry into the study and the informed consent process should be recorded in the subject's source documents. The original consent form, signed and dated by the subject and by the person consenting the subject prior to the subject's entry into the study, must be maintained in the Investigator's study files.

123 Subject confidentiality

The Primary Investigator and Celgene affirms the subject's right to protection against invasion of privacy. In compliance with United States federal regulations, Celgene requires the Primary Investigator to permit Celgene's representatives and, when necessary, representatives of the FDA or other regulatory authorities to review and/or copy any medical records relevant to the study in accordance with local laws.

Should direct access to medical records require a waiver or authorization separate from the subject's statement of informed consent, it is the responsibility of the Primary Investigator to obtain such permission in writing from the appropriate individual.

124 Study records requirements

The Primary Investigator must ensure that the records and documents pertaining to the conduct of the study and the distribution of the study drug be retained for as long as needed to comply with national, international and site specific regulations (generally 2 years after discontinuing clinical development or last marketing approval). This applies to copies of CRFs and source documents including but not limited to hospital records; clinical and office charts; laboratory notes; memoranda; subject's diaries or evaluation checklists; SAE reports; pharmacy dispensing records; recorded data from automated instruments; copies or transcriptions certified after verification as being accurate copies; microfiches; photographic negatives, microfilm, or magnetic media; x-rays; subject files; and records kept at the pharmacy, at the laboratories, and at medico-technical departments involved in the clinical study; documents regarding subject treatment and study drug accountability; and original signed informed consents. The Investigator agrees to adhere to the document/records retention procedures by signing the protocol.

125 Premature discontinuation of study

The Primary Investigator as well as Celgene have the right to discontinue this study at any time for reasonable medical or administrative reasons in any single center. Possible reasons for termination of the study could be but are not limited to:

- Unsatisfactory enrollment with respect to quantity or quality.
- Inaccurate or incomplete data collection.

- Falsification of records.
- Failure to adhere to the study protocol.

Any possible premature discontinuation would be documented adequately with reasons being stated, and information would have to be issued according to local requirements (e.g., IRB/EC, regulatory authorities, etc.).

13 RESPONSIBILITIES

13.1 Primary Investigator

The Primary Investigator is responsible for performing the following tasks:

- Coordinating, developing, submitting, and obtaining approval for the protocol as well as its subsequent amendments.
- Taking responsibility for the overall conduct of the study, and for monitoring the progress of the study.
- Reviewing and ensuring reporting of Serious Adverse Events (SAE)

14 PATIENTS WITH PROGRESSIVE DISEASE ON THE CONTROL ARM

Patients on the placebo control arm without GVAX vaccine with evidence of progressive disease by criteria defined in this protocol, who were in CR (defined as no measurable M-spike, immunofixation negative and bone marrow plasma cells <5%) but no longer meet the criteria for CR, or patients who were in nCR (no measurable M-spike, and a positive serum immunofixation) who develop measurable M-protein or free light chains in the serum or urine, or patients who were MRD negative who subsequently become MRD positive, can be evaluated, and potentially considered for roll over to the vaccine arm, provided they meet criteria for enrollment, and at the clinical discretion of the PI.

APPENDICES

APPENDIX 1: ECOG PERFORMANCE STATUS SCALE

SCORE	DESCRIPTION
0	Fully active, able to carry on all pre-disease performance without restriction.
1	Restricted in physically strenuous activity but ambulatory and able to carry out work of a light or sedentary nature, e.g., light house work, office work.
2	Ambulatory and capable of all self-care but unable to carry out any work activities. Up and about more than 50% of waking hours.
3	Capable of only limited self-care, confined to bed or chair more than 50% of waking hours.
4	Completely disabled. Cannot carry on any self-care. Totally confined to bed or chair.
5	Dead.

For list of Treatment Assignment Stratification prognostic indicators, see Appendix IV.

APPENDIX 2: TUMOR CLASSIFICATION

Diagnostic Criteria for Multiple Myeloma

Major Criteria

1. Plasmacytomas on tissue biopsy
2. Bone marrow plasmacytosis ($> 30\%$ plasma cells)
3. Monoclonal immunoglobulin spike on serum electrophoresis IgG > 3.5 g/dL or IgA > 2.0 g/dL; kappa or lambda light chain excretion > 1 g/day on 24 hour urine protein electrophoresis.

Minor criteria:

1. Bone marrow plasmacytosis (10 to 30% plasmacells)
2. Monoclonal immunoglobulin present but of lesser magnitude than given under major criteria
3. Lytic bone lesions
4. Normal IgM < 50 mg/dL, IgA < 100 mg/dL or IgG < 600 mg/dL

Any of the following sets of criteria will confirm the diagnosis of multiple myeloma:

- Any two of the major criteria
- Major criterion 1 plus minor criterion b, c, or d

- Major criterion 3 plus minor criterion a or c
- Minor criterion a, b and c or a, b and d

International Staging System for Multiple Myleoma

Stage I

- Albumin ≥ 3.5 g/dL AND
- Beta-2-microglobulin <3.5 mg/L

Stage II

Neither stage I nor stage III

Stage III

- Beta-2-microglobulin >5.5 mg/L

Durie-Salmon Staging of Multiple Myeloma

Stage I

All of the following must be present:

- Hemoglobin > 10.5 g/dL or hematocrit $>32\%$
- Serum calcium level normal
- Low serum myeloma protein production rates as evidenced by all of the following:
 - IgG peak < 5 g/dL
 - IgA peak < 3 g/dL
 - Bence Jones protein < 4 g/24 h
- No bone lesions

Stage II

All patients who do not meet criteria for Stage I or III are considered Stage II.

Stage III

One of the following abnormalities must be present:

- Hemoglobin < 8.5 g/dL, hematocrit $< 25\%$
- Serum calcium > 12 mg/dL
- Very high serum or urine myeloma protein production rates as evidenced by one or more of the following:
 - IgG peak > 7 g/dL
 - IgA peak > 5 g/dL
 - Bence Jones protein > 12 g/24 h
 - > 3 lytic bone lesion on bone survey (bone scan not acceptable)

Subclassification

A: Serum creatinine < 2.0 mg/dL
B: Serum creatinine > 2.0 mg/dL

APPENDIX 3: CRITERIA FOR DISEASE EVALUATION

The serum and urine M-protein levels obtained at baseline will be used as the reference baseline for calculation of increases or decreases in the M-protein level. The M-protein levels from the time of diagnosis will also be obtained, and response calculations using that value as baseline will also be performed in secondary analyses.

Definitions of Response

Responses will be defined as per the modified International Uniform Response Criteria for myeloma.⁵²

Response sub category	Response criteria ^a
sCR	CR as defined below plus normal FLC ratio and absence of clonal cells in bone marrow ^b by immunohistochemistry or immunofluorescence ^c
CR	Negative immunofixation on the serum and urine and disappearance of any soft tissue plasmacytomas and $\leq 5\%$ plasma cells in bone marrow ^b
nCR	Serum and urine M-protein undetectable. Immunofixation positive.
VGPR	Serum and urine M-protein detectable by immunofixation but not on electrophoresis or 90% or greater reduction in serum M-protein plus urine M-protein level $<100\text{mg per 24 h}$.
PR	$\geq 50\%$ reduction of serum M-protein and reduction in 24-h urinary M-protein by $\geq 90\%$ or to $<200\text{mg per 24 h}$. If the serum and urine M-protein are unmeasurable, ^d a $\geq 50\%$ decrease in the difference between involved and uninvolved FLC levels is required in place of the M-protein criteria. If serum and urine M-protein are unmeasurable, and serum free light assay is also unmeasurable, $\geq 50\%$ reduction in plasma cells is required in place of M-protein, provided baseline bone marrow plasma cell percentage was $\geq 30\%$. In addition to the above listed criteria, if present at baseline, a $\geq 50\%$ reduction in the size of soft tissue plasmacytomas is also required.
SD ^e	Not meeting criteria for CR, VGPR, PR or progressive disease
PD	Any one or more of the following criteria: Increase of 25% from lowest confirmed response value in one or more of the following criteria: 
 • Serum M-protein (absolute increase must be $\geq 0.5\text{ g/dL}$) • Serum M-protein increase $\geq 1\text{ g/dL}$, if the lowest Mcomponent was $\geq 5\text{ g/dL}$ • Urine M-protein (absolute increase must be $\geq 200\text{ mg/24h}$)

	
 • In patients without measurable serum and urine M-protein levels, the difference between involved and uninvolved FLC levels (absolute increase must be >10 mg/dL) • In patients without measurable serum and urine M-protein levels and without measurable involved FLC levels, bone marrow plasma-cell percentage irrespective of baseline status (absolute increase must be $\geq 10\%$) • Appearance of a new lesion(s), $\geq 50\%$ increase from nadir in SPD of >1 lesion, or $\geq 50\%$ increase in the longest diameter of a previous lesion >1 cm in short axis • $\geq 50\%$ increase in circulating plasma cells (minimum of 200 cells per μL) if this is the only measure of disease
Relapse from CR	
Any of the following criteria:
 
 • Reappearance of serum or urine M-protein by immunofixation or electrophoresis • Development of $\geq 5\%$ plasma cells in the bone marrow 
Appearance of any other sign of progression (ie, new plasmacytoma, lytic bone lesion, or hypercalcemia)

Relapse from MRD-negative CR	
Any one or more of the following criteria:
 
 • Loss of MRD negative state (evidence of clonal plasma cells on NGF or NGS, or positive imaging study for recurrence of myeloma) • Reappearance of serum or urine M-protein by immunofixation or electrophoresis 
Development of $\geq 5\%$ clonal plasma cells in the bone marrow; Appearance of any other sign of progression (ie, new plasmacytoma, lytic bone lesion, or hypercalcemia)

Abbreviations: CR, complete response; FLC, free light chain; PR, partial response; SD, stable disease; sCR, stringent complete response; VGPR, very good partial response; PD, progressive disease; MRD, minimal residual disease.

- All response categories require two consecutive assessments made at any time before the institution of any new therapy; all categories also require no known evidence of progressive or new bone lesions if radiographic studies were performed. Radiographic studies are not required to satisfy these response requirements.
- Confirmation with repeat bone marrow biopsy not needed.
- Presence/absence of clonal cells is based upon the k/l ratio. An abnormal k/l ratio by immunohistochemistry and/or immunofluorescence requires a minimum of 100 plasma cells for analysis. An abnormal ratio reflecting presence of an abnormal clone is k/l of 44:1 or 1:2.
- Refer to "Practical details of response evaluation" for definitions of measurable disease.
- SD is not recommended for use as an indicator of disease.

Practical details of response evaluation

Definitions of measurable disease

Response criteria for all categories and subcategories of response except CR are applicable only to patients who have 'measurable' disease defined by at least one of the following three measurements:

1. Serum M-protein ≥ 1 g/dl (≥ 10 gm/l)[10 g/l]
2. Urine M-protein ≥ 200 mg/24 h
3. Serum FLC assay: Involved FLC level ≥ 10 mg/dl (≥ 100 mg/l) provided serum FLC ratio is abnormal

